8.2.6. Clinical Benefit Rate (CBR)

[figure not shown]
Clinical benefit rate is the proportion of patients who achieve overall tumor response (confirmed CR or PR) or stable disease (SD) lasting for at least 24 weeks from randomization. Tumor assessments after the initiation of new anticancer therapy will not be included when determining CBR.

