4.2.2 Enrollment and Randomization of Patients to Treatment

Once eligibility is confirmed, patients will be randomized to a treatment group according to the randomization schedule. All patients must commence treatment with investigational products no later than 14 days after randomization. Patients who do not meet the eligibility criteria will not be randomized in the study, but may be rescreened up to two times at the Investigator's discretion.

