8 EFFICACY AND SAFETY ASSESSMENTS

8.1 Efficacy Assessment

8.1.1 Clinical Endpoints and Definitions

There are 2 co-primary endpoints in this study: independently-adjudicated PFS and OS. All patients randomized will be evaluated.

The secondary efficacy endpoints include Investigator-assessed PFS, ORR, DOR, and CBR (CR, PR or SD \geq 24 weeks), time to intervention for symptomatic metastatic CNS disease, and health outcomes assessments.

Progression-free Survival

Progression-free survival is determined programmatically from adjudicated PD, defined as the interval from the date of randomization until the first date on which recurrence, progression (per RECIST v1.1 [[Appendix 7](#)]) or death due to any cause, is documented, censored at the last assessable evaluation, or at the initiation of new anticancer therapy. It is not necessary to confirm disease progression.

Overall Survival

Overall survival is defined as the time from randomization to death due to any cause.

Objective Response Rate

The ORR is defined as the proportion of patients demonstrating either a CR or PR per RECIST v1.1 ([Appendix 7](#)) as their best overall response during the study. It is not necessary to confirm response.

Duration of Response

The DOR is measured from the time at which measurement criteria are first met for CR or PR (whichever status is recorded first) until the first date on which recurrence or PD or death is objectively documented, taking as a reference for PD the smallest measurements recorded since enrollment, per RECIST v1.1 ([Appendix 7](#)). The duration of overall complete response is measured from the time measurement criteria are first met for CR until the first date that recurrent disease is objectively documented.

Clinical Benefit Rate

The CBR is defined as the proportion of patients who achieved overall tumor response (CR or PR) or SD for at least 24 weeks. Stable disease is measured from enrollment until the criteria for disease progression or response are met, per RECIST v1.1 ([Appendix 7](#)).

Time to Intervention for Symptomatic CNS Disease

Time to intervention for symptomatic metastatic CNS disease is defined as the date of initiation of intervention or therapy for symptomatic CNS disease determined by the investigator to be due to CNS metastasis. This may include brain, leptomeningeal and epidural metastases including epidural spinal cord compression arising from tumor growth in the epidural space.

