- i. Timing for tumor assessments and health outcomes assessments (EORTC QLQ-C30, EORTC QLQ-BR23 and EQ-5D-5L) at the end of every 6 weeks (±3 days) is intended to reflect the end of every second cycle of study treatment. However, if cycles move off schedule for any reason, these assessments should remain every 6 weeks starting from Cycle 1/Day 1 during the active treatment phase. Tumor assessments will continue every 6 weeks until documented disease progression or death, regardless of whether the patient is continuing study treatment or has discontinued study treatment. The scans must be obtained and reviewed prior to start of the next cycle. For patients who show a CR on one scan and on a confirmatory scan obtained 6 weeks later, the frequency of subsequent scans may be reduced at the discretion of the investigator to no less than one scan every 12 weeks.
- j. Serious adverse events (SAEs) must be reported starting at the time of signing informed consent. All AEs including SAEs must be reported from initiation of study treatment and must continue to be followed for 28 days after last administration of investigational product.
- k. Cancer therapies evaluated at the safety follow-up contact and at the long-term follow-up contact include anti-cancer medications, cancer-related radiotherapy and cancer-related surgery/procedures since last contact.
- l. Tumor testing for HER2 gene amplification or overexpression will be performed by a central laboratory using HercepTest™ and possibly FISH analysis using IQFISH pharmDx™. ER/PR status will be determined using pharmDx™ kit. Either primary breast cancer tissue (e.g., from prior surgical resection) or other breast cancer-containing tissue (e.g., from biopsy or excision of cancer-containing lymph node or metastatic lesion) is acceptable for central HER2 testing (see Section 8.2.1.1).
- m. If a pregnancy test needs to be repeated during screening, a urine pregnancy test will suffice.
- n. Hematology panel: differentials (basophils, eosinophils, lymphocytes, monocytes, neutrophils), hematocrit, hemoglobin (Hb), international normalized ratio (INR), mean corpuscular hemoglobin (MCH), mean corpuscular hemoglobin concentration (MCHC), mean corpuscular volume (MCV), platelet count, prothrombin time (PT), activated partial thromboplastin time (aPTT), red blood cell count (RBC), red blood cell distribution width (RDW), white blood cell count (WBC) with differential.

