Stable disease is measured from the start of the treatment (in randomized studies, from date of randomization) until the criteria for progression are met, taking as reference the smallest sum on study (if the baseline sum is the smallest, this is the reference for calculation of PD). The clinical relevance of the duration of SD varies in different studies and diseases. If the proportion of patients achieving SD for a minimum period of time is an endpoint of importance in a particular study, the protocol should specify the minimal time interval required between two measurements for determination of SD. Note: The DOR and SD as well as the PFS are influenced by the frequency of follow-up after baseline evaluation. It is not in the scope of this guideline to define a standard follow-up frequency. The frequency should take into account many parameters including disease types and stages, treatment periodicity and standard practice. However, these limitations of the precision of the measured endpoint should be taken into account if comparisons between studies are to be made.

Appendix 8

Health Outcomes Assessment: EORTC QLQ-C30

ENGLISH

EORTC QLQ-C30 (version 3)

We are interested in some things about you and your health. Please answer all of the questions yourself by circling the number that best applies to you. There are no "right" or "wrong" answers. The information that you provide will remain strictly confidential.

Please fill in your initials:
 Your birthdate (Day, Month, Year):
 Today's date (Day, Month, Year): 31

	Not at All	A Little	Quite a Bit	Very Much
1. Do you have any trouble doing strenuous activities, like carrying a heavy shopping bag or a suitcase?	1	2	3	4
2. Do you have any trouble taking a long walk?	1	2	3	4
3. Do you have any trouble taking a short walk outside of the house?	1	2	3	4
4. Do you need to stay in bed or a chair during the day?	1	2	3	4
5. Do you need help with eating, dressing, washing yourself or using the toilet?	1	2	3	4

During the past week:

	Not at All	A Little	Quite a Bit	Very Much
6. Were you limited in doing either your work or other daily activities?	1	2	3	4
7. Were you limited in pursuing your hobbies or other leisure time activities?	1	2	3	4
8. Were you short of breath?	1	2	3	4
9. Have you had pain?	1	2	3	4
10. Did you need to rest?	1	2	3	4
11. Have you had trouble sleeping?	1	2	3	4
12. Have you felt weak?	1	2	3	4
13. Have you lacked appetite?	1	2	3	4
14. Have you felt nauseated?	1	2	3	4

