8.2.1. Progression Free Survival (PFS)

Progression free survival (PFS) is defined as the time interval from the date of randomization until the first date on which recurrence, progression (per RECIST v1.1), or death due to any cause, is documented. It is not necessary to confirm disease progression.

All tumor assessments and deaths collected will be used except in the following 2 cases:

1. If a subject misses 2 or more consecutive assessments immediately prior to the documentation of PD or death the subject will be censored at the last assessment prior to the missed visits (following the FDA guidance on clinical trial endpoints for the approval of cancer drugs and biologics).
2. For subjects that started a new anti-cancer therapy, all tumor assessments and deaths after the start date of new anti-cancer therapy will be excluded from the analysis.

After taking into account the two conditions listed above, subjects without documented PD or death, including those who dropped out, will be censored at their last tumor assessment. Patients who did not have any tumor assessments after the screening visit will be censored on the randomization date.

Assessment of PFS will be performed by a blinded, independent, central review of tumor assessments for all patients at Screening, and then after every 6 weeks from first dose of investigational product, regardless of treatment schedule modification (e.g., dose delay), until documented disease progression or death. PFS will be assessed using the Response Evaluation Criteria in Solid Tumors (RECIST v1.1).

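### As the SAP and protocol read together, stable disease that ends in progression at the week-24 scan can count as clinical benefit, and always does once dosing starts 3 or more days after randomization

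*SAP*

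**What the plan says.** **Threshold and start of the clock.** SAP 8.2.6 defines CBR as the proportion with a confirmed CR or PR, or with "stable disease (SD) lasting for at least 24 weeks from randomization". It does not state the end date of SD, and it does not ask for a progression-free scan at or after week 24.

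**End of the clock.** Protocol 8.1.1, under Clinical Benefit Rate: "Stable disease is measured from enrollment until the criteria for disease progression or response are met". Protocol Appendix 7, where it sets out how long SD lasts: "Stable disease is measured from the start of the treatment (in randomized studies, from date of randomization) until the criteria for progression are met".

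**Scan timing.** SAP 8.2.1 places scans "after every 6 weeks from first dose of investigational product, regardless of treatment schedule modification". Footnote i of Protocol Appendix 1 gives the ±3-day window and describes the timing as "intended to reflect the end of every second cycle of study treatment".

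**Start delay.** Protocol 4.2.2: "All patients must commence treatment with investigational products no later than 14 days after randomization".

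**Status of CBR.** SAP 8.3 and 8.3.2 make it descriptive, with no alpha. It is reported from both central and investigator assessments and compared by a stratified CMH test.

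**The concern.** A 24-week SD criterion is usually understood to mean that disease was still controlled at 24 weeks. Here the threshold coincides with a scheduled scan, the scan clock starts later than the SD clock, and SD is credited up to the day progression is found. The scan that shows treatment has failed can therefore be the one that completes the 24 weeks.

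Two things are at stake. The reported CBR can include patients already progressing at the landmark scan, in both arms and under both readers. And for patients dosed promptly, classification depends on whether the scan was booked a day or two early or late, in an open-label trial. No hypothesis test with allocated alpha is affected.

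**Working it through.** **1. Check of the planning figures used for size.** SAP 2.6 gives 419 PFS events for a hazard ratio of 0.70, alpha 0.01 and about 85% power, with medians of 34.7 weeks (experimental) and 24.3 weeks (control). Taking alpha as two-sided, Freedman's formula gives

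events = (2.576 + 1.036)² × [(1 + 0.70)/(1 − 0.70)]² = 13.05 × 32.11 ≈ 419.

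This reproduces the stated number (Schoenfeld's formula gives 411). The ratio of medians, 24.3/34.7 = 0.70, agrees. The documents give no planning figure for CBR.

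**2. Where the scans fall, in days from randomization.** Date = nominal day from first dose + scan offset (−3 to +3) + start delay (0 to 14).

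- Week-24 scan: earliest 168 − 3 + 0 = 165; latest 168 + 3 + 14 = 185.
- Week-18 scan: latest 126 + 3 + 14 = 143.

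**3. When progression at the week-24 scan still scores as 24 weeks of SD.** With SD ending at the progression date, the patient counts if 168 + offset + delay ≥ 168, that is, if offset + delay ≥ 0. The smallest offset is −3, so any delay of 3 days or more satisfies this for every in-window scan.

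For shorter delays, the share of possible scan days that qualify is as follows. The even spread of scan days is an assumption.

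| Start delay | Scans spread over −3 to +3 | Scans only at −3 to 0 |
|---|---|---|
| 0 days | 4/7 = 57% | 1/4 = 25% |
| 1 day | 5/7 = 71% | 2/4 = 50% |
| 2 days | 6/7 = 86% | 3/4 = 75% |
| 3 days or more | 100% | 100% |

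The second column is a stress test: Protocol 8.1.2 wants scans obtained before the next cycle starts, which favours early scanning. If delay were uniform over 0 to 14 days (an assumption, since only the maximum is stated), the averages would be (4/7 + 5/7 + 6/7 + 12)/15 = 94% and (0.25 + 0.50 + 0.75 + 12)/15 = 90%.

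**4. Ceiling on the inflation.** With exponential PFS, S(t) = exp(−ln 2 × t/median).

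- Control: S(18) − S(24) = 0.598 − 0.504 = 0.094.
- Neratinib: S(18) − S(24) = 0.698 − 0.619 = 0.079.

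**5. Effect on the arm difference**, using the progression-free proportion as a proxy for CBR.

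- No week-24 progressor counted: 61.9% − 50.4% = 11.5 points.
- All of them counted: 69.8% − 59.8% = 10.0 points.

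The inflation is larger in the control arm, so the gap narrows.

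**The case against.** **The SAP sentence does not itself say this.** That is correct. SAP 8.2.6 is silent on the end date, and a programmer might instead use the last scan showing SD. But the protocol states the end date in two places, and the SAP offers nothing else. The last-SD-scan reading also has its own fault: with no start delay, a patient stable on an in-window scan at day 165 would fail the 168-day test.

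**The rule follows the RECIST appendix, and PFS and duration of response also run to documented progression.** True, and for a duration that is the normal convention. For a binary landmark it has the side effect shown above. The same appendix says that, where SD of a minimum length is an endpoint of importance, the protocol should specify the minimum interval between measurements. Neither document does so for CBR.

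**Stronger readings that the documents do not support.** A reader might infer that most week-24 progressors are scored as benefit. That depends on the distribution of start delay, which is not given; with early scans and dosing on the day of randomization, only 25% would be. A reader might take 8 to 9 points as the expected overstatement. It is a ceiling, because it includes deaths, progression found earlier on unscheduled scans, and confirmed responders, who count anyway. A reader might also suspect that the rule favours neratinib; the illustration points slightly the other way. Lastly, sensitivity to a day or two of scheduling applies only at delays of 0 to 2 days. At longer delays the result is consistent, but every such patient counts.

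**Conclusion.** The point holds as a defect in the combined definition. An SD patient whose week-24 scan shows progression counts as clinical benefit whenever start delay plus scan offset is zero or more: always at delays of 3 days or more, and according to scan date at 0 to 2 days. This follows from the stated rules and needs no distributional assumption.

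The size is less certain. The ceilings of 9.4% (control) and 7.9% (neratinib) rest on exponential PFS with the planned medians. The true inflation is smaller by an amount that the documents do not allow one to calculate. CBR is descriptive and both arms are affected, so the consequence is an overstated secondary rate. The co-primary conclusions are untouched. It is worth correcting because the correction is cheap and the rate is reported under two readers.

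**What to change.** In SAP 8.2.6, keep the randomization clock and define the SD component of CBR as follows: at least one assessment of SD or better on or after day 165 from randomization (24 weeks less the 3-day scan window), with no progression at or before that assessment. State also that:

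- a first progression at the week-24 scan does not count;
- patients with no qualifying assessment, including those never dosed, count as no clinical benefit unless they are confirmed responders;
- the same rule applies to central and investigator CBR.

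Keeping the clock at randomization matters because a clock starting at Cycle 1 Day 1 is undefined for randomized patients who never take a dose. An in-window week-18 scan falls no later than day 143, so it cannot qualify by accident.

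The cost is one SAP passage and a matching clarification in Protocol 8.1.1, with no new data. Reported CBR will be somewhat lower. With no start delay, SD documented at day 165 is credited up to 3 days short of a literal 24 weeks; this tolerance is deliberate, so that a scan done early within its window is not penalised.

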8.3. Analysis Methods

The significance levels allocated to the co-primary efficacy endpoints are 0.01 for PFS and 0.04 for OS. However, once the null hypothesis for PFS is rejected at $\alpha = 0.01$ at the time of the primary analysis then OS can be tested at the overall significance level of 0.05. The additional alpha propagated to the OS endpoint will not be spent at the interim OS analysis (Ye, 2013). The interim boundary for OS will remain the same as the boundary using the Lan-DeMets alpha spending function with overall $\alpha=0.04$ based on the actual information fraction (number of deaths as a proportion of the 378 target number of deaths). The time to CNS intervention will be tested after PFS and OS. If PFS is not significant and OS is, then time to CNS will be tested at $\alpha=0.04$; if both are significant, then time to CNS will be tested at $\alpha=0.05$. Unless OS is significant at the interim analysis, time to CNS intervention will not be tested at the primary PFS analysis (interim OS), and will only be tested after OS is significant at the final OS analysis (Figure 1).

Test of all other secondary endpoints are descriptive.

Figure 1: Testing Schema

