2.6. Sample Size Determination

The co-primary endpoints will be analyzed using an overall Type I error rate of 0.01 for PFS and 0.04 for OS. To detect a hazard ratio (experimental vs. control) of 0.70 with approximately 85% power, 419 PFS events (PD/Deaths) are required to be observed; this assumes a median (ITT) PFS of 8.0 months (34.7 weeks) for the experimental arm (neratinib plus capecitabine) and 5.6 months (24.3 weeks) for the control arm (lapatinib plus capecitabine).

It is expected that the 419th event will be observed at approximately 26 months after the first subject is enrolled, which would correspond to approximately half of the death events needed to be observed. At this time, an interim analysis on OS will also be performed. For the OS endpoint, a group sequential method will be employed to maintain the overall Type I error rate at 0.04. Specifically, Lan DeMets alpha spending function approximating the O’Brian-Fleming boundaries will be calculated to create appropriate critical values to which the log rank statistic will be compared (De Mets and Gordon Lan, 1994). If 50% of the deaths are observed at the interim OS analysis, the boundary using the Lan-DeMets alpha spending function is shown in Table 1 for OS interim analysis.

Table 1: Spending Function

Information Fraction	Expected Death Events	Study Month	Boundary (Reject H_0)	2-Sided Significance Level*
50%	185	26	3.066	0.002
100%	378	50	2.058	0.039

* This significance level relates to the 0.04 alpha allocation to OS but will be updated if the entire 0.05 can be allocated to OS.

These boundaries are designed to detect a hazard ratio (experimental vs. control) of 0.725 with approximately 85% power. Overall, 378 OS events (deaths) are required to be observed; this assumes a median (intent to treat [ITT]) OS of 30.3 months for the experimental arm (neratinib plus capecitabine) and 22.0 months for the control arm (lapatinib plus capecitabine).

Approximately 600 subjects will be enrolled and randomized equally between the two treatment arms. This sample size assumes a 1% drop out rate per 12 months (52 weeks) equally distributed between the treatment arms for the PFS endpoint.

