8.3.2. Secondary Efficacy Analyses

The secondary endpoints of ORR, CBR and duration of response will be assessed using the centrally reviewed tumor assessments as well as the investigator tumor assessments. The secondary endpoint of time to intervention for symptomatic CNS disease will only use the investigator-reported data.

The treatment difference in the secondary efficacy endpoint of investigator assessed PFS will be assessed with the product limit estimate of the median time to event. Differences between treatment groups will be examined using a log rank test statistic stratified by hormone receptor status, number of prior HER2-directed regimen in the metastatic setting, visceral disease status, and geographic region strata (similar to the analyses for the primary endpoints). All time-to-event endpoints including time to intervention for symptomatic CNS disease will be displayed using a Kaplan-Meier survival plot.

For the secondary endpoints of ORR and CBR the subjects included in the analyses are those that had measurable disease (per RECIST v1.1) at screening. Any tumor assessments after the start of new anti-cancer therapy will not be included in the analyses for these two endpoints. The treatment difference in the secondary efficacy endpoints of ORR and CBR will be analyzed using a Cochran-Mantel-Haenzel (CMH) Chi-square test, stratified on hormone receptor status, number of prior HER2-directed regimens in the metastatic setting, geographic region and disease category (visceral vs. non-visceral only).

Duration of response will be summarized by treatment group for the patients that responded. If there are patients that continue to respond, they will be censored at their last tumor assessment and a Kaplan-Meier analysis will be done to estimate the duration of response.

With the exception of the CNS endpoint, which will be tested only after the null hypothesis is rejected for OS; all other secondary endpoints are descriptive analyses and will be done at the time of the primary PFS analysis.

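### Time to CNS intervention is tested at the full 0.04 or 0.05 at whichever look OS first succeeds, with no group-sequential boundary of its own

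*SAP*

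**What the plan says.** SAP 2.6 splits the error as an "overall Type I error rate of 0.01 for PFS and 0.04 for OS". Table 1 there gives OS a boundary at each of its two looks, headed "2-Sided Significance Level": z = 3.066 (0.002) at 185 deaths and 2.058 (0.039) at 378 deaths. The interim coincides with the primary PFS analysis, "which would correspond to approximately half of the death events needed to be observed".

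SAP 8.3 passes alpha on to the CNS endpoint. It is tested at 0.04 if OS alone is significant and at 0.05 if PFS and OS both are. On timing it states: "Unless OS is significant at the interim analysis, time to CNS intervention will not be tested at the primary PFS analysis (interim OS". If OS is not significant at the interim, CNS is tested only after OS is significant at the final analysis. SAP 8.3.2 repeats the gate: "With the exception of the CNS endpoint, which will be tested only after the null hypothesis is rejected for OS". The test is a stratified Gray's test. All other secondary endpoints are descriptive.

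Lan-DeMets spending is specified for OS only. SAP 2.6, 8.3, 8.3.2 and 10, and section 3 of the supplemental SAP, give no boundary, spending function or information fraction for CNS.

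**The concern.** Gating CNS behind OS controls error across endpoints. It does not control the gated endpoint's own error when the look at which it is tested depends on the data. An early OS success tends to occur when the interim data happen to favour neratinib. If the CNS statistic is positively correlated with the OS statistic, it shares that fluctuation and is then tested at full level. When OS does not succeed early, CNS gets its chance on the final data.

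The SAP recognises the issue for OS: the recycled 0.01 is withheld from OS at the interim. Yet at that same look, if PFS and OS are both significant, CNS is tested at the full 0.05, while OS itself has to meet about 0.002.

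CNS is the only secondary endpoint with a formal test, so both the error rate of that claim and the power available for it are at stake.

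**Working it through.** **1. The plan's own OS figures.** Inputs from SAP 2.6: "These boundaries are designed to detect a hazard ratio (experimental vs. control) of 0.725 with approximately 85% power"; a target of 378 deaths; 1:1 allocation; two-sided alpha 0.04.
- Freedman: (2.054 + 1.036)² × (1.725/0.275)² = 9.549 × 39.35 = 376 deaths. Schoenfeld: 4 × 9.549/(ln 0.725)² = 370. Both are within 3% of 378.
- Lan-DeMets O'Brien-Fleming-type spending of 0.04 at half information gives z = 3.090 and 2.061, two-sided 0.0020 and 0.0393. The printed levels reproduce. The printed z values differ slightly (together they spend 0.0403), which does not affect this point.

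**2. Chance of an early OS win at HR 0.725.** The expected interim statistic is 0.3216 × √185/2 = 2.187. The crossing probability is 1 − Φ(3.066 − 2.187) = 19% with the printed boundary. It is 1 − Φ(3.125 − 2.187) = 17% with the boundary recomputed at 185/378. Taking exactly half of the deaths (189) with 3.066 gives 20%.

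**3. CNS tested once, at the look where OS first succeeds (CNS null).** This was simulated with 2 million draws of OS and CNS statistics at two looks. Between-look correlation is √t with t about one half. The OS–CNS correlation is assumed, because the documents give none. Two-sided CNS error stays at or below 0.04 or 0.05 at every correlation from 0 to 1, within simulation error. Error in favour of neratinib, nominal 0.025:

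| OS–CNS correlation | Maximum over OS effect | At OS HR 0.725 |
|---|---|---|
| 0 | 0.025 | 0.022 |
| 0.1 | 0.026 | 0.024 |
| 0.3 | 0.027 | 0.026 |
| 0.5 | 0.029 | 0.029 |
| 0.6 | 0.030 | 0.030 |

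For nominal 0.02 (total 0.04) the maxima are 0.0216 at correlation 0.3 and 0.0231 at 0.5.

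**4. Power of the single test.** The documents give no CNS event rate or effect, so these are assumptions: control-arm CNS hazard λ of 0.5, 1.0 or 1.5% per month, cause-specific HR 0.70, uniform 24-month accrual of 600 patients, exponential deaths with the SAP medians (30.3 and 22.0 months) as the competing event, and no dropout. Expected events per arm are 300 × the mean over entry time s of [λ/(λ+δ)] × [1 − exp(−(λ+δ)(T − s))], where δ is the death hazard and T = 26 or 50 months. The neratinib arm uses 0.70λ. Power is Φ(0.3567 × √events/2 − c), with c = 1.960 for the SAP rule. The boundary at total 0.05 and 50% information is 2.963 at the interim and 1.969 at the final.

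| λ | Events, month 26 / 50 | Fraction | SAP rule, interim / final | Own boundary, interim / final |
|---|---|---|---|---|
| 0.5% | 27.5 / 55.4 | 0.50 | 15% / 26% | 2% / 26% |
| 1.0% | 53.2 / 103.9 | 0.51 | 25% / 44% | 5% / 44% |
| 1.5% | 77.3 / 146.5 | 0.53 | 35% / 58% | 8% / 58% |

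First row as an example: 0.3567 × √27.5/2 = 0.935, and Φ(0.935 − 1.960) = 15%.

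**5. If CNS were repeated at full level at the final analysis.** Error is 1 − P(|Z₁| < c, |Z₂| < c) with correlation √t. At t = 0.5 this is 0.067 for 0.04 and 0.083 for 0.05. For t from 0.4 to 0.7 it runs from 0.070 down to 0.061, and from 0.086 down to 0.076. These are maxima, reached when an interim OS success is nearly certain. At OS HR 0.725 and nominal 0.05, the two-sided error with a repeat is about 0.050 at correlation 0 and 0.048 at 0.5.

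**The case against.** The strongest reply is that SAP 8.3 describes alternatives: CNS is tested at the interim if OS succeeds there, and otherwise at the final. On that natural reading there is one CNS test, and two-sided error, the scale the SAP uses, is held. This stands. What remains is a modest excess in the favourable direction, which depends on an unknown correlation, and the loss of power after an early OS win.

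A reader might infer that CNS error reaches 0.083. That requires a second full-level test after a failed interim test. The visible text neither provides for one nor excludes it, and Figure 1 (the testing schema) does not appear in the copy available for review. The figure is the consequence of an unstated procedure, not of the plan as written.

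A reader might also take it as given that the interim CNS test uses half the data. The 185/378 fraction is for deaths. The CNS fraction of 50 to 53% comes from the assumed hazards.

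Finally, Protocol 4.1 allows the end of study to be declared earlier, for example if the OS endpoint is met, although the protocol synopsis says no interim for early stopping is planned. If follow-up closed after an early OS win, no repeat test could inflate the error. A strict interim CNS boundary would then be the only CNS test, at 2 to 8% power. This is a real cost of the remedy and the fix has to deal with it.

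**Conclusion.** The concern holds in limited form. The only formally tested secondary endpoint has two possible test times and no boundary of its own. Under the single-test reading, two-sided error does not exceed 0.04 or 0.05. Error in favour of neratinib can exceed alpha/2 when OS and CNS statistics are positively correlated: up to about 0.026 to 0.030 against 0.025 for assumed correlations of 0.1 to 0.6, and none at zero correlation.

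The practical loss arises when OS succeeds early. The one CNS test then falls on interim data, with little more than half the power it would have at the final under the assumed hazards and HR. The 0.067 and 0.083 figures apply only if CNS is re-tested at full level, and the text should settle that before anyone sees interim CNS data. OS and PFS error control is not affected. The point should be fixed, but it does not threaten the primary conclusions.

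**What to change.** Add a paragraph to SAP 8.3 with these elements:
- Time to CNS intervention has its own Lan-DeMets O'Brien-Fleming-type spending function at its available alpha, based on CNS-event information, with the projected total number of CNS events stated.
- At 50% CNS information the nominal two-sided levels would be 0.0031 and 0.0490 for a total of 0.05 (z = 2.963 and 1.969), or 0.0020 and 0.0393 for a total of 0.04 (z = 3.090 and 2.061). They are recomputed at the actual fraction.
- CNS is tested against this boundary when OS is rejected. If it is not rejected at the interim, it is tested again at the final analysis.
- CNS follow-up continues to that final analysis even if OS succeeds early.

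The cost is one paragraph and a much stricter interim threshold: interim CNS power falls from 15–35% to about 2–8% at HR 0.70. Final power is essentially unchanged, so the benefit depends on the final CNS analysis being carried out. If that cannot be guaranteed, a simpler alternative is to state that CNS is tested once and to name the analysis. Naming one fixed analysis removes the dependence on when OS succeeds.
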